4.3.2 Exploratory Analyses/Sensitivity Analysis

In order to explore potential differences in the change in BAD from baseline to Visit 4 and PGI-I at Visit 4 across population subgroups, subgroup analyses will be performed for the ITT population on the following factors assessed at the baseline of the initial study: Age at onset of motor symptoms (<6 years vs. ≥ 6 years), DBS (Deep Brain Stimulation, Yes vs. No), Region (US vs. Europe), and Duration of disease (>5 years vs. ≤ 5 years).

Besides analysis for the ITT population, the efficacy analyses will also be repeated for outcomes defined based on BAD total score and PGI-I for the PP population as sensitivity analyses.

As a sensitivity analysis, the statistical analysis on the change in the BAD total score from baseline to Visit 4 and PGI-I at Visit 4 will be repeated with the missing data being imputed as described in section 3.5 based on the ITT population.

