3.2 Determination of Sample Size and Study Power

There was no formal sample size and power calculation for this study. All patients who completed TIRCON2012V1 study were invited to enroll in the extension study. Among the 89 subjects randomized in TIRCON2012V1 study, 76 completed the study and 68 subjects were subsequently enrolled in this extension study (44 originally randomized to the deferiprone group and 24 in the placebo group).

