3.6 Statistical Software and Level of Significance

All statistical analyses will be performed using SAS (version 9.3 or higher) on Windows operating system. Null hypotheses tested are that there are no differences in true parameter between comparison groups, unless otherwise stated. A two-sided *p*-value of 0.05 will be used as the significance level for the determination of statistical significance in all statistical tests.

4 Statistical Analyses

The efficacy endpoints are defined as follows:

All patients:

- Change in the BAD total score from baseline (defined as prior to the start of deferiprone therapy) to Visit 4, as assessed by central evaluation of videotapes
- Proportion of patients with improved or unchanged BAD scale total score between baseline and Visit 4 (responder analysis, responders defined as change in BAD total score to be ≤ 0)
- Change from baseline to Visit 4 in BAD scale score per body region (eyes, mouth, neck, trunk, and each upper and lower extremity), as assessed by central evaluation of videotapes
- PGI-I score at Visit 4
- Proportion of patients showing an improvement on PGI-I at Visit 4 (responder analysis, responders are defined as patients whose conditions have not deteriorated; patients who have “no change”, or are “minimally improved”, “much improved” or “very much improved” in the PGI-I questionnaire at the last study visit)

The time points for these efficacy endpoints are defined as follows:

- For patients who received deferiprone in the initial study, the baseline visit of that study will be treated as the baseline visit of TIRCON2012V1-EXT as well. Thus, Visit 1 of the extension study (Week 0) will be Year 1.5 (month 18), and Visit 4 (Week 78) will be Year 3 (month 36).
- For patients who received placebo in the initial study, Visit 1 of the extension study (Week 0) will be the baseline visit. Thus, Visit 4 (Week 78) will be Year 1.5 (month 18).

Patients who received placebo in initial study:

For this group only, for each measure, the changes seen between the start and completion of the initial study (TIRCON2012V1) (i.e., following 18 months on placebo) will be compared against the changes seen between the start and completion of extension study (TIRCON2012V1-EXT) (i.e., following 18 months on deferiprone), as follows:

- Comparison of change in BAD total score from baseline to completion of the initial study vs. change in BAD total score from baseline to completion of the extension study

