4.3.1 Efficacy Endpoints

All patients:

For the efficacy measures of BAD (total score and by body region) and PGI-I, the value at each of the measurement time points defined in section 4 will be determined and summarized using descriptive statistics for all patients on DFP treatment. Similar data will also be presented by the treatment group received in initial study.

A paired t-test will be used to assess the statistical significance of the changes in these efficacy outcomes from baseline to the end of study (Visit 4, month 18 or 36 as defined in section 4).

For the BAD total score and for PGI-I, the proportions of patients determined to be responders at the end of study (Visit 4) will be calculated and presented along with 95% confidence intervals.

The mean trajectory of BAD (total score and by body region) and PGI-I by time will be plotted. The longitudinal trend for BAD total score and by body region will be explored by the MMRM model with time modelled as a continuous variable as defined in section 4 for all time points where patients were on DFP.

Patients who received placebo in initial study:

For the efficacy measures of BAD (total score and by body region) and PGI-I, the value at each of the measurement time points defined in section 4 will be determined and summarized using descriptive statistics for each study period.

A paired t-test will be used to compare the change in BAD (total score and by body region) between the start and completion of the initial study to that between the start and completion of the extension study. The same test will be repeated for the PGI-I data.

The incidence of changes in DBS settings and outcome impacting medication use as well as the frequency of PRN drug or rescue medication use will be tabulated and compared between the initial study and the extension study. If statistically significant imbalances are detected, they will be adjusted accordingly for the comparison of changes in BAD and PGI-I between the initial study and the extension study by using the MMRM model as defined in section 4.

For the BAD total score and for PGI-I, McNemar's test will be used to compare the proportion of responders in the initial study with the proportion of responders in the extension study.

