	Visit	Placebo-DFP (N=xx)	DFP-DFP (N=xx)
Responder in PGI-I n (%)	Month 6	xx (xx.x)	xx (xx.x)
	Month 12	xx (xx.x)	xx (xx.x)
	Month 18	xx (xx.x)	xx (xx.x)
	Month 24	xx (xx.x)	xx (xx.x)
	Month 30	xx (xx.x)	xx (xx.x)
	Month 36	xx (xx.x)	xx (xx.x)

Similar Table 14.2.1.13a will be based on PP population

Table 14.2.1.14 Proportions of responders in PGI-I at each follow-up visit for all patients on DFP – ITT population

	Visit	DFP (N=xx)
Responder in PGI-I n (%)	Month 6	xx (xx.x)
	Month 12	xx (xx.x)
	Month 18	xx (xx.x)
	Month 24	xx (xx.x)
	Month 30	xx (xx.x)
	Month 36	xx (xx.x)

Similar Table 14.2.1.14a will be based on PP population

Table 14.2.1.15 Efficacy endpoints analysis for all patients on DFP: change in value at the end of study (Visit 4) – ITT population

	Visit	Score n Mean (SD)	Change from Baseline n Mean (SD)	p-value [§]
BAD Total Score	Baseline	xx xx.xx (xx.x)		
	Visit 4	xx xx.xx (xx.x)	xx xx.xx (xx.x)	0.xxxx
PGI-I	Visit 4		xx xx.xx (xx.x)	0.xxxx
Eyes score	Baseline	xx xx.xx (xx.x)		
	Visit 4	xx xx.xx (xx.x)	xx xx.xx (xx.x)	0.xxxx
Repeat for other body regions

§ p-value from paired t-test

Similar Table 14.2.1.15a will be based on PP population

Similar Table 14.2.1.15s will be based on missing data imputed as sensitivity analysis

Similar Tables 14.2.1.15.1 and 14.2.1.15.2 will be based on ITT population and Age at onset of motor symptoms (Age <6 vs. Age ≥6)

Similar Tables 14.2.1.15.3 and 14.2.1.15.4 will be based on ITT population and DBS (Deep Brain Stimulation Yes vs. No)

Similar Tables 14.2.1.15.5 and 14.2.1.15.6 will be based on ITT population and Region (US vs. Europe)

Similar Tables 14.2.1.15.7 and 14.2.1.15.8 will be based on ITT population and Duration of disease at baseline (>5 years vs. ≤5 years)

Table 14.2.1.16 Efficacy endpoints analysis for all patients on DFP: proportions of responders in BAD total score and PGI-I at the end of study (Visit 4) – ITT population

	Visit	(N=xx)
Responder in BAD total score n (%) (95% CI)	Visit 4	xx (xx.x) (xx.x, xx.x)
Responder in PGI-I n (%) (95% CI)	Visit 4	xx (xx.x) (xx.x, xx.x)

Similar Table 14.2.1.16a will be based on PP population

Similar Table 14.2.1.16s will be based on missing data imputed as sensitivity analysis

Table 14.2.1.17 Trend analysis by MMRM model on BAD total score and by body region for all patients – ITT population

Dependent Variable	Time slope	95% CI of the Slope	p -value
BAD Total Score	xx.x	(xx.xx xx.x)	0.xxxx
Eyes	xx.x	(xx.xx xx.x)	0.xxxx

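### The subgroup analysis is meant to explore differences between subgroups, but the planned tables test only the change within each subgroup and never estimate the difference

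*SAP*

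**What the plan says.** SAP 4.3.2 states the purpose: "In order to explore potential differences in the change in BAD from baseline to Visit 4 and PGI-I at Visit 4 across population subgroups". It names four factors taken at the baseline of the initial study. The first two are "Age at onset of motor symptoms (<6 years vs. ≥ 6 years), DBS (Deep Brain Stimulation, Yes vs. No"); the others are region (US or Europe) and disease duration (above 5 years or not). The section names no method for comparing the levels of a factor.

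The output is defined in SAP section 5 and in the table shells of section 7. There are eight tables, one per level, each a copy of Table 14.2.1.15. The notes under that shell read "Similar Tables 14.2.1.15.1 and 14.2.1.15.2 will be based on ITT population and Age at onset of motor symptoms" and "Similar Tables 14.2.1.15.3 and 14.2.1.15.4 will be based on ITT population and DBS", with matching notes for the other two factors. The shell shows n, mean (SD), change from baseline and one p-value column, footnoted "p-value from paired t-test". SAP 4.3.1 describes the same test: "A paired t-test will be used to assess the statistical significance of the changes in these efficacy outcomes".

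SAP 3.6 adds that a two-sided p-value of "0.05 will be used as the significance level for the determination of statistical significance in all statistical tests". SAP 3.2 gives the size: "68 subjects were subsequently enrolled in this extension study (44 originally randomized to the deferiprone group and 24 in the placebo group"). It also says that no formal power calculation was made.

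**The concern.** The question concerns the difference between two levels; the planned test concerns each level on its own. For BAD, the paired t-test asks whether the mean change within the level is zero. For PGI-I, which has no baseline score, the shell also shows a paired t-test p-value, but the SAP does not say which value the score is tested against.

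Each pair of tables therefore gives a reader two p-values to set side by side, under a SAP that applies 0.05 to every test. The natural but invalid inference is that the disease changed in one subgroup and not in the other. In a study of 68 patients cut in two, that pattern can arise readily when the true change is the same in both levels. At stake are statements about, for example, early-onset versus later-onset patients that no planned estimate supports.

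**Working it through.** **What the plan gives.** There is no subgroup power figure to reproduce. The one count that can be checked agrees: 44 + 24 = 68. Sixty-eight is used below as the upper limit for the ITT population.

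**What is assumed.** The documents give no SD, no expected change and no subgroup sizes. The true standardised change d (mean change divided by its SD) is taken as equal in both levels, so there is no real subgroup difference. Three splits of 68 are shown. Unequal splits are plausible for age at onset: Protocol 1.1.1 says that most cases are classical and that classical disease usually begins before age 6, which is the SAP's cut.

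**Formula.** For a level of size n, the power p of the two-sided 0.05 paired t-test comes from the noncentral t distribution with n − 1 degrees of freedom and noncentrality d√n. The two levels contain different patients, so the tests are independent and

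P(exactly one significant) = p₁(1 − p₂) + p₂(1 − p₁).

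**Worked cases at d = 0.4.**
- 34/34: p₁ = p₂ = 0.620, giving 2 × 0.620 × 0.380 = 0.471.
- 54/14: p₁ = 0.823 and p₂ = 0.284, giving 0.823 × 0.716 + 0.284 × 0.177 = 0.589 + 0.050 = 0.64.

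**Chance that exactly one level is significant, same true change in both:**

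| d | 34/34 | 50/18 | 54/14 |
|---|---|---|---|
| 0 | 9.5% | 9.5% | 9.5% |
| 0.3 | 48% | 53% | 55% |
| 0.4 | 47% | 58% | 64% |
| 0.5 | 31% | 49% | 58% |
| 0.6 | 14% | 34% | 45% |
| 0.8 | 1% | 11% | 21% |

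**What drives it.** At 34/34 the rate is already 31% to 48% for d of 0.3 to 0.5, so limited power is enough to produce it. Inequality raises the rate and tilts it. At d = 0.4 and 54/14, only the larger level is significant in 59% of cases and only the smaller in 5%; at 34/34 it is 24% each way.

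**With a direct contrast.** A between-level test has a false-positive rate of about 5% per factor (4.8% to 5.3% in a simulation with common d of 0, 0.345 and 0.5 and splits near 50/50 and 75/25). Over four unadjusted tests, treated as independent, the chance of at least one is 1 − 0.95⁴ = 18.5%.

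**Precision of the contrast.** The unadjusted 95% CI half-width, in SD units, is t(0.975; 66) × √(1/n₁ + 1/n₂), with t = 1.997:
- 34/34: 1.997 × 0.2425 = 0.48
- 54/14: 1.997 × 0.2999 = 0.60
- 58/10: 1.997 × 0.3424 = 0.68

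**The case against.** The best defence is that the SAP calls the analysis exploratory, contains no rule for declaring a subgroup effect, and prints n, mean and SD for the change in every level. A reader can derive the unadjusted difference and its interval from those. The subgroup cuts concern secondary efficacy endpoints in a study whose primary objective is safety. All of this stands, and it limits the consequence. It does not supply the comparison that SAP 4.3.2 sets out to make. Nor can a reader adjust the derived difference for initial-study group. That matters because Visit 4 is month 36 for patients on deferiprone throughout and month 18 for those switched from placebo, and the subgroup tables pool them. The SAP does print a between-group t-test in Table 14.2.3.1, so the omission here does not follow from a general policy.

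Four stronger readings are tempting, and the documents do not support them:
- *Unequal subgroup sizes alone cause the problem.* Equal halves already give 31% to 48% at 0.3 to 0.5 SD.
- *Discordant results will be frequent whatever the truth.* The rate is 9.5% with no change and falls to 1% to 21% at 0.8 SD. Protocol 1.1.1 describes a progressive disease, so a large change cannot be excluded.
- *The SAP plans to infer subgroup effects from paired p-values.* It states no such inference; the risk lies in how the tables will be read.
- *A proper contrast would reveal a differential drug effect.* All patients receive deferiprone in the extension, so without a concurrent control the contrast compares change over time only.

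**Conclusion.** The point holds as a minor one. The stated aim and the planned output do not match: SAP 4.3.2 asks about differences between levels, and nothing in the SAP estimates or tests one for these factors. The misleading pattern arises in 31% to 64% of cases per factor for a common change of 0.3 to 0.5 SD and splits from 34/34 to 54/14, against about 5% for a direct test. That range rests on an assumed effect size, assumed subgroup sizes and all 68 patients being analysed. Limited power is the main cause, and unequal sizes make it worse. The mismatch itself rests on the text and table shells and needs none of these assumptions.

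**What to change.** For each of the four factors, add to SAP 4.3.2 and the shells:
- the between-level difference in mean BAD total score change to Visit 4 with a 95% CI, from an ANCOVA with baseline BAD and initial-study group as covariates;
- the same contrast for the Visit 4 PGI-I score, with baseline BAD as the baseline covariate, as SAP section 4 already specifies for its PGI-I models.

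State that these contrasts are exploratory and unadjusted for multiplicity (about 18.5% familywise if all four are tested). State also that any remark on subgroup differences will rest on them and not on the within-level p-values, and that they describe differences in change over time, not in drug effect. If the PGI-I p-value stays, name its null value. The within-level p-values may stay or go; removing them is a matter of preference.

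The cost is some SAP wording and four contrasts per outcome, with no new data. The intervals will be wide, with a half-width of about 0.5 to 0.7 SD before covariate adjustment, so most contrasts will be inconclusive.

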4.4 Safety Analyses

The safety endpoints include:

- Adverse events (AEs): Frequency, severity, time to onset, duration, and relatedness to study product
- Serious adverse events (SAEs): Frequency, severity, time to onset, duration, and relatedness to study product

-
- Number of discontinuations due to AEs
 - Hematology assessments
 - Blood chemistry assessments
 - ECG assessments

All safety data collected will be presented in listings and summary tables or graphs to give an overview of the safety findings. All safety endpoints will be analyzed based on the safety population. For patients continuing on deferiprone in the extension study, this time period will be from the start of TIRCON2012V1 to the completion of TIRCON2012V1-EXT; for those who received placebo in the initial study and are switching to deferiprone in the extension study, it will be from the start to the completion of the extension study.

For those patients who do not follow the scheduled time window exactly for each visit or withdraw from the study early, the following time window will be employed to classify the safety data into each scheduled visit according to the time elapsed from the first medication date (date of exposure) to the assessment date:

Month 1.5 visit: 0.75 to <2.25 months

Month 3 visit: 2.25 to <4.5 months

Month 6 visit: 4.5 to <9 months

Month 12 visit: 9 to <15 months

Month 18 visit: 15 to <21 months

Month 24 visit: 21 to <27 months

Month 30 visit: 27 to <33 months

Month 36 visit: 33 to <39 months

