2.1 Primary Objective

To evaluate the long-term safety and tolerability of deferiprone in patients with PKAN.

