Completed	xx	xx	xx
Withdrawn	xx	xx	xx

Table 14.1.3 Subject exposure to study medication – ITT population

	Group		
	Placebo-DFP (N=xx)	DFP-DFP (N=xx)	Overall (N=xx)
Subjects Exposed	xx	xx	xx
Total Exposure (person-years)	xxx.x	xxx.x	xxx.x
Length of Exposure (years)			
Mean (SD)	xx.xx (xx.x)	xx.xx (xx.x)	xx.xx (xx.x)
Median	xx.x	xx.x	xx.x
(Min, Max)	(xx.x, xx.x)	(xx.x, xx.x)	(xx.x, xx.x)
Duration of Exposure [n(%)]			
>= 1 month	xx (xx)	xx (xx)	xx (xx)
>= 6 months	xx (xx)	xx (xx)	xx (xx)
Repeat for 9, 12, 15, 18 months

Table 14.1.4 Number of patients enrolled by study site – ITT population

Country	Site	Group		
		Placebo-DFP	DFP-DFP	Overall
xxx	000x	xx	xx	xx
...	...	xx	xx	xx
Total	x	xx	xx	xx

Table 14.1.5 Summary of the reasons for not completing the study – ITT population

		Group		
		Placebo-DFP (N=xx)	DFP-DFP (N=xx)	Overall (N=xx)
Reason	Detail	n (%)	n (%)	n (%)
Adverse event	Ccccc	xx (xx)	xx (xx)	xx (xx)
	Ccccc	xx (xx)	xx (xx)	xx (xx)
Voluntary withdrawal	Ccccc	xx (xx)	xx (xx)	xx (xx)
	Ccccc	xx (xx)	xx (xx)	xx (xx)
Lost to follow up	Ccccc	xx (xx)	xx (xx)	xx (xx)
	Ccccc	xx (xx)	xx (xx)	xx (xx)
Investigator decision	Ccccc	xx (xx)	xx (xx)	xx (xx)
	Ccccc	xx (xx)	xx (xx)	xx (xx)
Protocol violation	Ccccc	xx (xx)	xx (xx)	xx (xx)
	Ccccc	xx (xx)	xx (xx)	xx (xx)
Worsening of the disease/ Lack of efficacy	Ccccc	xx (xx)	xx (xx)	xx (xx)
	Ccccc	xx (xx)	xx (xx)	xx (xx)
Other	Ccccc	xx (xx)	xx (xx)	xx (xx)
	Ccccc	xx (xx)	xx (xx)	xx (xx)
Total		xx (xx)	xx (xx)	xx (xx)

Demographics and baseline characteristics tables

Table 14.1.6 Summary of demographics data at baseline of initial study – ITT population

	Group			
	Placebo-DFP (N=xx)	DFP-DFP (N=xx)	Overall (N=xx)	DFP vs Placebo p -value [§]
Age (years) (Mean ± SD) (Minimum, Median, Maximum)	xx.x ± xx.x (xx.x, xx.x, xx.x)	xx.x ± xx.x (xx.x, xx.x, xx.x)	xx.x ± xx.x (xx.x, xx.x, xx.x)	0.xxxx
Sex: n (%) Female Male	xx (xx) xx (xx)	xx (xx) xx (xx)	xx (xx) xx (xx)	0.xxxx
Racial Origin: n (%) White Black Asian Native American Native Hawaiian or Other Pacific Islander Multi-Racial	xx (xx) xx (xx) xx (xx) xx (xx) xx (xx) xx (xx)	xx (xx) xx (xx) xx (xx) xx (xx) xx (xx) xx (xx)	xx (xx) xx (xx) xx (xx) xx (xx) xx (xx) xx (xx)	0.xxxx
Ethnic Origin: n (%) Hispanic/Latino Other	xx (xx) xx (xx)	xx (xx) xx (xx)	xx (xx) xx (xx)	0.xxxx

§ T-test for means and Fisher's exact test for percentages

Similar Table 14.1.6a will be based on PP population

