Table 14.2.2.9 Efficacy endpoints analysis with MMRM model: Least square mean (LSM) change in score from baseline to Visit 4 for patients on placebo in initial study – ITT population

	Visit	Placebo in TIRCON (N=xx)	DFP in TIRCON- EXT (N=xx)	DFP - Placebo LSM Difference (95% CI)	p-value
BAD	Change from baseline to Visit 4 Mean (SD)	xx.xx (xx.x)	xx.xx (xx.x)	xx (xx.x xx.x)	0.xxxx
PGI-I	Score at Visit 4 Mean (SD)	xx.xx (xx.x)	xx.xx (xx.x)	xx (xx.x xx.x)	0.xxxx
BAD Eyes	Change from baseline to Visit 4 Mean (SD)	xx.xx (xx.x)	xx.xx (xx.x)	xx (xx.x xx.x)	0.xxxx
Repeat for other body regions

Table 14.2.3.1 Comparison of change in BAD total score from baseline to month 18 for patients on DFP in initial study and patients on placebo in initial study but switched to DFP in the extension study – ITT population

	Visit	DFP in TIRCON (N=xx)	DFP in TIRCON- EXT (N=xx)	p -value [§]
BAD n Mean (SD) Median (Min, Max) p -value [§]	Baseline	xx xx.xx (xx.x) xx.x (xx.x, xx.x)	xx xx.xx (xx.x) xx.x (xx.x, xx.x)	
	Month 6	xx xx.xx (xx.x) xx.x (xx.x, xx.x) 0.xxxx	xx xx.xx (xx.x) xx.x (xx.x, xx.x) 0.xxxx	0.xxxx
	Month 12	xx xx.xx (xx.x) xx.x (xx.x, xx.x) 0.xxxx	xx xx.xx (xx.x) xx.x (xx.x, xx.x) 0.xxxx	0.xxxx
	Month 18	xx xx.xx (xx.x) xx.x (xx.x, xx.x) 0.xxxx	xx xx.xx (xx.x) xx.x (xx.x, xx.x) 0.xxxx	0.xxxx

§ T-test

Safety outcomes tables

Table 14.3.1.1 Overall summary of adverse events – safety population

	Treatment Group
	DFP (N=xx)
Number of subjects with at least one AE	xx (xx%)
Number of subjects with at least one SAE	xx (xx%)
Number of subjects with at least one severe AE	xx (xx%)
Number of subjects with at least one ADR	xx (xx%)
Number of deaths	xx (xx%)
Number of subject withdrawn	xx (xx%)
Number of subject withdrawals due to AE	xx (xx%)

Table 14.3.1.2 Summary of adverse events – safety population

	DFP	
	Exposure (subject-years): x.xx	
	Total Subjects Exposed: xx	
	Total Events: xxx	
	Total Subjects Reporting: xx	
System		
Organ Class	N Subjects (%)	N Events (Rate/100 patient years)
Preferred Term		
CCCCCC	x (x.x)	x (x.xx)
Ccccc	x (x.x)	x (x.xx)
Ccccc	x (x.x)	x (x.xx)
Ccccc	x (x.x)	x (x.xx)
.....	x (x.x)	x (x.xx)

Table 14.3.1.3 Summary of adverse events related to iron deficiency – safety population

	DFP	
	Exposure (subject-years): x.xx	
	Total Subjects Exposed: xx	
	Total Events: xxx	
	Total Subjects Reporting: xx	
Preferred Term	N Subjects (%)	N Events (Rate/100 patient years)
Ccccc	x (x.x)	x (x.xx)
Ccccc	x (x.x)	x (x.xx)
Ccccc	x (x.x)	x (x.xx)

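### AE rates, Visit 4 laboratory summaries and exposure-duration rows do not separate deferiprone experience after Month 18 from the first 18 months

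*SAP*

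**What the plan says.** SAP 2.1 gives the primary objective: "To evaluate the long-term safety and tolerability of deferiprone in patients with PKAN". SAP 3.2 states that "There was no formal sample size and power calculation for this study" and reports 68 enrolled patients, "44 originally randomized to the deferiprone group and 24 in the placebo group".

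SAP 4.4 sets the safety observation period. For patients continuing on deferiprone, "this time period will be from the start of TIRCON2012V1 to the completion of TIRCON2012V1-EXT"; for switchers it is the extension alone. SAP 3.5 dates exposure from the first deferiprone dose, which for continuers lies in the initial study. SAP 3.3 limits the Safety population to patients dosed in the extension.

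SAP 4.4.1 plans AE counts, percentages and a rate per 100 patient-years, with no split by cohort or time on drug. The shells in SAP Section 7 match:

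- **AEs.** Table 14.3.1.1, whose first row is "Number of subjects with at least one AE", has one DFP group. Tables 14.3.1.2 to 14.3.1.8 add the rate, also for DFP as a whole.
- **Laboratory, Visit 4.** Tables 14.3.2.1.2, 14.3.2.1.3, 14.3.2.2.2 and 14.3.2.2.3 compare baseline with Visit 4 or end of study, cohorts combined.
- **Exposure.** Table 14.1.3 has Placebo-DFP, DFP-DFP and Overall columns. Its duration rows are 1 month or more and 6 months or more, then "Repeat for 9, 12, 15, 18 months".

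The efficacy shells, by contrast, give many results by Placebo-DFP and DFP-DFP.

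**The concern.** Continuers supply all the deferiprone experience after Month 18, yet the AE tables merge it with everyone's first 18 months. A toxicity that emerges late and one that appears early and fades can give the same entry. AE percentages also mix patients observed for up to 18 months with patients observed for up to 36.

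The Visit 4 laboratory tables have the same fault in another form: a single mean change, or a single shift count, combines a switcher's value at Month 18 with a continuer's at Month 36. The duration rows of Table 14.1.3 do not describe months 18 to 36.

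At stake is whether the report can state AE and SAE rates for exposure beyond 18 months, a large part of what the extension adds to its primary objective.

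**Working it through.** The plan states no person-time or power figure to reproduce. The one check available agrees: 44 + 24 = 68.

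**Inputs.** 44 continuers and 24 switchers (SAP 3.2); up to 3 years and 1.5 years on deferiprone respectively (SAP Section 4, time points). Full follow-up is assumed unless stated. All AE rates below are illustrative and not from the documents.

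**Maximum patient-years**
- Total: 44 × 3 + 24 × 1.5 = 132 + 36 = 168.
- Months 0 to 18: 68 × 1.5 = 102.
- After Month 18: 44 × 1.5 = 66, continuers only; 66/168 = 39%.
- If 10% to 30% leave evenly through the extension, each leaver gives half the period on average, so the later time is 66 × 0.95 = 62.7 to 66 × 0.85 = 56.1.

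**Pooled rate** = (102 × r1 + 66 × r2)/168, with r1 the rate before and r2 after Month 18, per 100 patient-years.
- Risk doubles, 10 then 20: (1020 + 1320)/168 = 13.9.
- Risk halves, 17.33 then 8.67: (1768 + 572)/168 = 13.9.

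**Pooled percentage**, constant 10 per 100 patient-years:
- Risk by 18 months: 1 − exp(−0.15) = 13.9% (its match with the rate above is coincidence).
- Risk by 36 months: 1 − exp(−0.30) = 25.9%.
- Table entry: (44 × 25.9 + 24 × 13.9)/68 = 21.7%, the risk at neither time.

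**Duration rows.** Extension entry requires completing the 18-month initial study (Protocol 4.2). With exposure dated as in SAP 3.5, nearly every continuer meets every row. SAP 4.1 refers to medication taken during the study, which could mean the extension alone. The rows would then fit, but would still not describe cumulative exposure beyond 18 months.

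**What a split could show.** With cut points at 6 and 18 months, the maximum patient-years are:

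| Cohort | 0 to 6 | >6 to 18 | >18 to 36 | Total |
|---|---|---|---|---|
| DFP-DFP | 22 | 44 | 66 | 132 |
| Placebo-DFP | 12 | 24 | 0 | 36 |
| Overall | 34 | 68 | 66 | 168 |

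- Zero events in 66 patient-years give a one-sided 95% upper bound of −ln(0.05)/66 = 4.5 per 100 patient-years.
- Power to detect a doubled rate after Month 18 (exact conditional binomial test, two-sided 0.05; late share of events 66/168 = 0.39 under no change, 132/234 = 0.56 under doubling) is about 14%, 30%, 60% and 95% for early rates of 5, 10, 20 and 50 per 100 patient-years.

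**Selection.** SAP 3.2 gives 89 randomised, 76 completing and 68 entering the extension, so 89 − 68 = 21 are outside the Safety population; their split by arm is not given. The continuers' first 18 months (66 of the 168 patient-years) therefore omit deferiprone patients who stopped early or did not enrol.

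**The case against.** The strongest reply is that much of the late experience is already visible.

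- SAP 4.4 classifies safety data by time since first deferiprone dose, to Month 36. Hematology, biochemistry, urinalysis, vital signs and weight have Month 24, 30 and 36 rows, with n; ECG appears at Months 18 and 36. Switchers end near Month 18, so the later rows come essentially from continuers. Per-patient laboratory plots are planned too.
- Table 14.1.3 also gives person-years and length of exposure by cohort.
- Table 14.1.5 gives withdrawals for adverse events by cohort (ITT population). Every continuer entered the extension, so that cohort's withdrawals fall after about Month 18.
- SAEs, AE withdrawals and deaths are listed and narrated. Time to onset is planned for AEs above 5% and those of special interest.
- Section 7 allows final tables to differ from the shells.

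The first three items stand. A reader might infer that the plan cannot show late safety at all, or that its laboratory tables hide it; the documents do not support that. Nor do they name a change in risk after 18 months as the primary question: the objective is long-term safety, and Protocol 3.2 speaks of patient-years of exposure.

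The rest does not close the AE gap. Time to onset and listings carry no person-time by period, so they give no rate. The only shell with time to onset, Table 14.3.1.8, is limited to adverse drug reactions above 5%, at least 4 of 68 patients. Freedom to vary a layout commits no one to a split that SAP 4.4.1 does not request.

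It is also fair that under constant risk the planned rate is correct, and that a split would have little power. AE reporting here is descriptive, so low power limits interpretation but does not argue against showing the periods.

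**Conclusion.** The point holds for three sets of outputs.

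1. AE and SAE percentages and rates are pooled over cohorts and time on drug, and opposite risk patterns can give the same rate.
2. The hematology and biochemistry Visit 4 change and shift tables mix Month 18 with Month 36.
3. The duration rows of Table 14.1.3 stop at 18 months and, under the SAP 3.5 dating rule, hardly discriminate among continuers.

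About 39% of planned deferiprone time (66 of 168 patient-years, or 37% to 38% with 10% to 30% loss) lies after Month 18 and has no AE rate of its own. The patient-years are maxima resting on full follow-up except where a loss is stated.

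This is a shortfall in presentation that should be corrected. No planned test is invalidated, and it does not show that late toxicity exists or would go unnoticed.

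**What to change.** 1. Add Placebo-DFP, DFP-DFP and Overall columns to Tables 14.3.1.1 to 14.3.1.8 and to the Visit 4 laboratory change and shift tables (14.3.2.1.2, 14.3.2.1.3, 14.3.2.2.2, 14.3.2.2.3).
2. Add one descriptive AE/SAE table by onset interval since first deferiprone dose (0 to 6, >6 to 18, >18 to 36 months), by cohort, with patients at risk, patient-years and rate. Footnote that the continuers' first 18 months come only from patients who completed the initial study and entered the extension. Their early rate is therefore likely biased low, and a higher later rate must not be read as a within-cohort rise in risk.
3. Add rows for at least 24, 30 and 36 months to Table 14.1.3, and state that duration runs from first deferiprone dose.

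The cost is programming: the cohort columns, first-dose date and windows to Month 36 are already defined. Cells will be small, so period comparisons stay descriptive.
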